## **10.3 Reporting Procedure for AEs, SAEs, and Pregnancy**

### **10.3.1 Adverse Events**

All AEs either observed by the Investigator or one of his/her medical collaborators, or reported by the subject spontaneously, or in response to a direct question, will be noted in the AE section of the subject's eCRF and source documentation. This applies to all AEs regardless of presumed relationship to the study treatment. Adverse events leading to discontinuation of study treatment must be collected.

If any AE is reported, the date of onset, relationship to disease under study, relationship to study treatment, any action taken, date of resolution (or the fact that it is still continuing or has become chronic), outcome, and whether the AE is serious or not, will be recorded. Use of colloquialisms and abbreviations should be avoided. Only 1 AE term should be recorded in the event field on the AE eCRF. Where possible, the Investigator should report a diagnosis rather than signs and symptoms or abnormal laboratory values. However, if a constellation of signs and/or symptoms cannot be medically characterized as a single diagnosis or syndrome at the

time of reporting, each individual event should be recorded on the AE eCRF. If a diagnosis is subsequently established, all previously reported AEs based on signs and symptoms should be nullified by the Investigator and replaced by one AE report based on the single diagnosis, with a starting date that corresponds to the starting date of the first symptom of the eventual diagnosis.

The AE reporting period begins at the time the ICF is signed by the subject. The AE reporting period ends at the study follow-up visit (Visit 24). Adverse events persisting at the time of study completion will be followed by the Investigator through contact with the subject until resolution or stabilization has occurred (or the subject is lost to follow-up and cannot be contacted) and recorded in the source documents. If the subject reports an AE, it is the Investigator's responsibility to acquire sufficient information in order to assess causality. This may require additional laboratory testing, physical examinations, telephone contacts, etc. In circumstances where the Investigator is unable to make contact with the subject, the Investigator must provide a written statement to Aurinia confirming that the subject is lost to follow-up.

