6.1.2 Safety Population

The safety population will consist of all subjects who receive at least 1 dose of study drug in the AURORA 2 study (n=216). The subjects in this group will be analyzed based on the treatment they received. Subjects who receive voclosporin treatment for more than 14 days will be assigned to the voclosporin arm irrespective of the arm they were randomized to.

Additional safety populations will be defined as follows:

- AURORA 1 safety population (all subjects who were treated in core study, n=356) and
- subjects who did not participate in AURORA 2 (n=140).

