6.3 Conventions

All data listings, summaries, figures and statistical analyses will be generated using SAS version 9.4 or higher¹.

Summaries will be presented by treatment group for all subjects. Treatment group labels will be displayed as follows:

- Placebo
- Voclosporin
- Overall

Columns to be included within the table shells are as follows:

Demography	Treatment group and overall
Baseline	Treatment group and overall
Disposition	Treatment group and overall
Efficacy	Treatment group
TEAEs	Treatment group
Other safety	Treatment group

Tables of events or medications will be ordered in descending frequency of subjects followed by (where applicable) events for the system organ class (or Anatomical Therapeutic Chemical Classification System [ATC] level 2 for medications) followed by the preferred term. Ordering will be for the voclosporin treatment group first followed by the placebo group and alphabetical thereafter.

Listings will be sorted in the following order: treatment group, subject, parameter, and visit unless otherwise stated. All data will be listed.

Continuous variables will be summarized by the number of non-missing observations, mean, median, standard deviation, and minimum and maximum. For all tabulations of changes from baseline data, the lower and upper 95% confidence limits for the mean for the individual treatments will be given.

QMD Ref: [REDACTED]	Effective: 12Aug2019	Governing QMD: [REDACTED]
Confidentiality Statement		
This document is the property of [REDACTED] and may not be duplicated, copied, altered or removed from company without prior approval from [REDACTED] or in compliance with [REDACTED].		

		Controlled Quality Management Document	
		Sponsor:	Aurinia Pharmaceuticals
		Protocol Number:	AUR-VCS-2016-02
STATISTICAL ANALYSIS PLAN. PHASE 2-3-4			

Categorical variables will be summarized by presenting the frequency and percent. Percentages will be based on the number of non-missing observations out of the subject population unless otherwise specified. For each variable, all categories will be shown. Zero frequencies (but not the percent) within a category will be presented.

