This document is the property of [REDACTED] and may not be duplicated, copied, altered or removed from company without prior approval from [REDACTED] or in compliance with [REDACTED].		

REF: [REDACTED]

		Controlled Quality Management Document	
		Sponsor:	Aurinia Pharmaceuticals
		Protocol Number:	AUR-VCS-2016-02
STATISTICAL ANALYSIS PLAN. PHASE 2-3-4			

- Serious TEAE by System Organ Class, Preferred Term and Severity
- Treatment-Related, Serious TEAE by System Organ Class and Preferred Term
- Treatment-Related, Serious TEAE by System Organ Class, Preferred Term and Severity
- Serious TEAE by System Organ Class and Preferred Term Leading to Dose Modification
- Serious TEAE by System Organ Class and Preferred Term Leading to Voclosporin/Placebo Discontinuation
- Disease-Related, Serious TEAE by System Organ Class and Preferred Term

The following displays of AURORA 2 TEAEs will also be presented:

- Treatment-Emergent Adverse Events by Descending Frequency of Preferred Term
- Non-Serious Treatment-Emergent Adverse Events Occurring at an Incidence of >2% by Descending Frequency, System Organ Class and Preferred Term
- Treatment-Emergent Adverse Events by Descending Difference of Preferred Term between Treatment Group
- Listing of Serious TEAE
- Listing of TEAE Resulting in Death
- Listing of Post-Treatment Adverse Events Resulting in Death

The following displays will include all TEAEs from the start of AURORA 1:

- TEAE by System Organ Class and Preferred Term by Year of Onset
- Treatment-Related TEAE by System Organ Class, Preferred Term and Year of Onset
- TEAE by System Organ Class and Preferred Term Leading to Dose Modification by year of onset
- Serious TEAE by System Organ Class and Preferred Term by Year of Onset
- Treatment-Related, Serious TEAE by System Organ Class and Preferred Term and Year of onset
- Serious TEAE by System Organ Class and Preferred Term Leading to Dose Modification by year of onset

The following displays will be presented for all randomized subjects from Aurora 1?

- TEAE by System Organ Class and Preferred Term
- Serious TEAE by System Organ Class and Preferred Term

QMD Ref: [REDACTED]	Effective: 12Aug2019	Governing QMD: [REDACTED]
Confidentiality Statement		
This document is the property of [REDACTED] and may not be duplicated, copied, altered or removed from company without prior approval from [REDACTED] or in compliance with [REDACTED].		

REF: [REDACTED]

		Controlled Quality Management Document	

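### The year-of-onset adverse event tables state no population or yearly denominator, and the all-randomized tables may mix unequal follow-up

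*SAP*

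**What the plan says.** The adverse event lists in SAP 6.12.1 contain a block introduced by "The following displays will include all TEAEs from the start of AURORA 1". It holds six displays by year of onset: all TEAEs, treatment-related, leading to dose modification, serious, treatment-related serious, and serious leading to dose modification. The first is "TEAE by System Organ Class and Preferred Term by Year of Onset". The block gives no population and no denominator for each year.

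The only general rule in the available text is in SAP 6.3: "Percentages will be based on the number of non-missing observations out of the subject population unless otherwise specified".

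A further block begins "The following displays will be presented for all randomized subjects from Aurora 1", and in the SAP that line ends in a question mark. It lists TEAEs and serious TEAEs by System Organ Class and preferred term, with no split by year and no stated time window. Earlier in the same section the SAP says that some tables will run from Month 0 to Month 36.

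SAP 6.1.2 gives 216 subjects in the AURORA 2 safety population, 356 treated in AURORA 1, and 140 who did not take part in AURORA 2. SAP 6.12.1.1 plans rates per 100 years of exposure using events from both studies and states no split by year.

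On follow-up, Protocol 5.2 requires completion of 52 weeks of AURORA 1 treatment. Protocol 5.5 allows withdrawal at any time without replacement. Protocol 5.6 asks subjects who stop study drug to keep attending visits to Month 36 if possible. Adverse event reporting closes at the follow-up visit, Visit 24 (Protocol 10.3.1).

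**The concern.** A percentage by year of onset can be read as risk in that year only if its denominator is the number of subjects who could have had an event recorded in that year. Entry to AURORA 2 required completion of Year 1, so all 216 subjects were observed through it. After entry, subjects can die, withdraw or be lost. If N stays at 216, those subjects count in the Year 2 and Year 3 denominators with no chance of contributing an event. The later percentages then fall even at a constant hazard, and a real rise with longer treatment can look flat. The pooled exposure-adjusted rate gives one figure over all years, so it cannot correct this.

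The all-randomized displays raise a different problem. If they cover Months 0 to 36, a crude percentage treats a subject seen for about one year like one seen for three. The arm comparison is then distorted if continuation into AURORA 2 differed by arm.

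Long-term safety is the primary objective and the adverse event profile is part of the primary endpoint. Among the listed adverse event displays, year of onset is the only breakdown that shows change over time.

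**Working it through.** **The plan's own counts.** 356 − 216 = 140, which agrees with SAP 6.1.2. The share of treated subjects without AURORA 2 participation is 140/356 = 39.3%. The documents give no loss rate and no continuation by arm, so every such rate below is an assumption.

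**By-year tables, N fixed at 216.** Let h be a constant yearly hazard and L the fraction of the starting number lost in each of Years 2 and 3, spread evenly within the year.

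- Event probability over a full year: F = 1 − exp(−h). With h = 0.30, F = 25.9%.
- Average event probability for a subject lost during the year: P = 1 − F/h = 1 − 0.2592/0.30 = 13.6%.
- Year 2 percentage = (1 − L)F + L·P.
- Year 3 percentage = (1 − 2L)F + L·P.

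| Assumed loss L per year | Year 1 | Year 2 | Year 3 | Year 3 / Year 1 |
|---|---|---|---|---|
| 0% | 25.9% | 25.9% | 25.9% | 1.00 |
| 5% | 25.9% | 25.3% | 24.0% | 0.93 |
| 10% | 25.9% | 24.7% | 22.1% | 0.85 |
| 15% | 25.9% | 24.1% | 20.2% | 0.78 |

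For example, at L = 10% Year 3 is 0.80 × 25.9% + 0.10 × 13.6% = 22.1%. The size hardly depends on the hazard: at h = 0.05 the Year 3 ratios are 0.93, 0.85 and 0.78. They follow the share of person-time still observed in Year 3, which is 1 − 1.5L = 0.925, 0.85 and 0.775.

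Solving the Year 3 formula for the hazard that returns 25.9%, a true rise of about 21% (L = 10%) or 35% (L = 15%) would look flat.

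**Effect of the alternatives.** Dividing Year 3 by subjects under observation at its start (N × (1 − L)) gives 24.0/0.95 = 25.3%, 22.1/0.90 = 24.6% and 20.2/0.85 = 23.7% (from unrounded values). Most of the dilution goes, and what remains comes from partial-year follow-up. A rate over observed person-years recovers the constant hazard.

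**Why the population must be named.** If 356 were the denominator, events in AURORA 2 subjects would show at 216/356 = 0.607 of their value on 216, even with no loss. The SAP does not say that 356 is used.

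**All-randomized displays, if they cover Months 0 to 36.** Taking one year of observation for each non-continuer, the unobserved share of nominal person-time is 140 × 2 / (356 × 3) = 280/1068 = 26%. With no drug effect and a fraction p continuing, the crude risk in an arm is p(1 − exp(−3h)) + (1 − p)(1 − exp(−h)). At h = 0.02 the two terms are 5.82% and 1.98%.

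- p = 70% vs 50%: 4.67% / 3.90% = 1.20.
- p = 65% vs 56%: 4.48% / 4.13% = 1.08.
- Equal continuation: 1.00.

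**The case against.** A reader might infer that the SAP fixes the full population as denominator in every year and so makes risk appear to fall with longer treatment. The documents do not support this.

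- **The fixed denominator is an inference.** The available text omits the page on which SAP 6.12.1 opens, and a rule could stand there. The 6.3 default also speaks of non-missing observations, so a subject who left before Year 3 could be read as having none for that year. This stands: the defect is an unstated denominator, with a default that points to a constant N.
- **The 140 non-continuers do not create a falling trend.** The all-randomized displays are not split by year, and all 216 subjects enter Year 2. The Month 0 to 36 window is itself an assumption for these displays. This stands, so the two problems have to be kept apart.
- **The net direction is uncertain.** The 216 exclude subjects who died or permanently stopped during Year 1. That selection can lower Year 1 and push the trend upward. This stands.
- **Loss may be small.** Subjects who stop study drug are asked to keep attending, and collection to Month 37 can offset Year 3 by at most about one month in twelve. This limits the size but does not supply a denominator.
- **The stated estimand compares arms.** Equal loss dilutes both arms alike, so arm comparisons within a year are biased only if loss differs by arm. Year-on-year trend is not named as the primary question. This stands and lowers the stakes.
- **Exposure-adjusted rates, withdrawals by arm and a listing of all adverse events are already planned.** They help an overall reading, but none gives a rate by year.

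**Conclusion.** The concern holds in a limited form. The available SAP text leaves the population and yearly denominator of the six year-of-onset displays unstated, its default implies the same N each year, and no planned rate is by year.

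At a constant hazard, Year 3 would read about 7, 15 or 22% below Year 1 if 5, 10 or 15% of the starting number left observation in each of Years 2 and 3, and no lower if nobody left. These losses are assumed. The figures isolate denominator dilution and do not predict the observed trend, which the selection of Year 1 completers can move the other way.

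The all-randomized displays are a separate, conditional problem. If they span Months 0 to 36, about 26% of nominal person-time is unobserved, and the crude risk ratio with no drug effect could be 1.08 to 1.20 under the unequal continuation assumed above. With equal continuation it is 1.00. The count of 356 is of treated subjects; the available text gives no randomized count.

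This does not show that the safety conclusions would be wrong. A better method is available at little cost for tables that bear on the primary objective.

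**What to change.** In SAP 6.12.1:

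1. Name the population for the year-of-onset displays.
2. Set each year's denominator to the subjects under adverse event observation at the start of that year, by arm.
3. Add events per 100 person-years of adverse event observation within each year, by arm, as an extension of 6.12.1.1. This handles the partial-year loss that item 2 leaves.
4. Resolve the question mark on the all-randomized block, state its time window, and report those displays as rates over observed person-time by arm.

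The cost is SAP wording, revised table shells and a few more columns. The visit and termination dates are already collected. The drawback is that denominators will differ between columns, which a footnote can explain.

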6.12.1.1 Exposure-Adjusted Incidence Rates

Tables showing the overall incidence rate, total number of subjects with a given event and total events per 100 years exposure will be produced. These tables will incorporate all events from AURORA 1 and AURORA 2.

All AEs will be listed.

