  - 2 Visit 15 assessments marked (-) will be provided from the results of the Week 52 Visit in the AURORA study.
  - 3 Subjects who discontinue therapy will attend their regularly scheduled study visits to the end of the study. Subjects who withdraw consent and terminate the study early should be advised to attend both Visit 23 and the Safety Follow-up Visit (Visit 24).
  - 4 Subjects will have a safety follow-up visit after the last dose of study drug, and an assessment of vital status at 6 and 12 months post study.
  - 5 Unscheduled visits/assessments can be done as needed. AEs, concomitant medications and verbal compliance check should be completed.
  - 6 Abbreviated physical examination only required. Height is not required.
  - 7 At sites that are able to meet the biopsy requirements, [REDACTED]
  - 8 During the study, in the event that a subject is noted to have a QTcF value exceeding 500 msec, or >60 msec more than baseline, the ECG will be repeated; see Section 9.1.4.1, [Procedures to Manage a Treatment-Emergent Increase in QTc](#).
  - 9 Laboratory assessments will be performed according to the schedule in Section 9.1.1, [Laboratory Assessments](#); subjects will be fasting for 8 hours on the day of study entry on Month 12 (Week 52/ End of Treatment Visit of the AURORA 1 study) and at Month 24 and Month 36 End of Study visit.
  - 10 Serum pregnancy test to be evaluated at central laboratory at Month 12 using AURORA 1 Visit 15 result, Month 24, and Month 36.
  - 11 Urine pregnancy test to be performed at Month 12 (AURORA 1 Visit 15) for subjects who consent for enrollment into the AURORA 2 continuation study. In addition, urine pregnancy tests to be performed at all other visits indicated (except Month 24 and Month 36 where serum pregnancy test is performed).
  - 12 AEs will be recorded after the subject signs the ICF.
  - 13 Concomitant medications include all herbal medicines and supplements taken by the subject.
  - 14 Compliance only.
  - 15 All subjects will continue to receive oral corticosteroids starting at the same dose as at the end of the AURORA 1 study. When clinically indicated, subjects are allowed to be completely titrated off of oral corticosteroids; the sites will contact the Medical Monitor if the dose of oral corticosteroids is to be increased.
  - 16 24-hour urine collection should begin 2 days prior to the scheduled study visit in order not to coincide with the FMV sampling due on the day of the study visit.

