6.2.9 Exposure to Study Drug

Exposure to study drug will be calculated from the date of last dosing minus the first day of dosing (in AURORA 2) + 1 for each prescribing record. Exposure will be summarized as the number of days on medication and mean daily dose. Mean daily dose will take into account periods where zero dose was prescribed.

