6.9 Exposure to Study Drug

Overall exposure to study drugs (number of days of exposure to study drugs and mean dose) will be presented for both the safety populations. Exposure will be based on prescribed dose. Exposure will not be summarized by visit but for the overall study duration in AURORA 1 and AURORA 2. Overall study drug exposure will be calculated from the first dose date in AURORA 1 to the last dose date in AURORA 2 plus 1. Care should be taken to not double-count days. It is expected that prescription records will cover each study day between randomization and the end of study (or early termination). Periods of zero dose will be assigned as such.

The following gives an example of a subject with 5 prescription records over the 3-year (1095 day) period.

Final prescription records that detail a zero dose will be removed.

Table 5.1 Exposure calculation example

Start Day	End Day	Dose (bid)	Duration
1	364	3	364 days
365	500	3	136 days
501	600	0	100 days
601	750	2	150 days
751	1095	3	345 days

For the purposes of analysis this subject will have ‘days on treatment’ calculated as 364+136+100+150+345=1095 days. Their mean daily dose will be:

$(364*3 + 136*3 + 100*0 + 150*2 + 345*3) / 1095 = 2.34$ caps BID (converted to 37.03mg per day).

Gaps between dosing records will be counted as a zero dose.

For subjects who are lost to follow-up, and for whom the last dose date from the termination record is unknown, the date of the last available visit will be used as the last dose date.

QMD Ref: [REDACTED]	Effective: 12Aug2019	Governing QMD: [REDACTED]
Confidentiality Statement		
This document is the property of [REDACTED] and may not be duplicated, copied, altered or removed from company without prior approval from [REDACTED] or in compliance with [REDACTED].		
REF: [REDACTED]		

		Controlled Quality Management Document	
		Sponsor:	Aurinia Pharmaceuticals
		Protocol Number:	AUR-VCS-2016-02
STATISTICAL ANALYSIS PLAN. PHASE 2-3-4			

Exposure to study drug will be summarized for the following:

- Voclosporin
- MMF
- Oral Corticosteroids.

Prescribed dose changes at visit intervals and overall will be summarized for voclosporin/placebo and for MMF.

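### Exposure-adjusted and by-year adverse event displays: events are not paired with a matching time at risk, so rates can rise with early stopping and yearly percentages can fall at constant risk

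*SAP*

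**What the plan says.** **Exposure-adjusted rates.** SAP 6.12.1.1 promises an overall incidence rate and says that the "total number of subjects with a given event and total events per 100 years exposure will be produced". It adds: "These tables will incorporate all events from AURORA 1 and AURORA 2". It does not define the years of exposure, give an event window after the last dose, or name the population.

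**Exposure.** SAP 6.2.9 defines AURORA 2 exposure: "Exposure to study drug will be calculated from the date of last dosing minus the first day of dosing (in AURORA 2) + 1". SAP 6.9 gives the two-study version: "Overall study drug exposure will be calculated from the first dose date in AURORA 1 to the last dose date in AURORA 2", plus 1. Interruptions stay in the day count as zero dose, but time after the last dose does not: "Final prescription records that detail a zero dose will be removed".

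**Follow-up.** Footnote 3 of the protocol's Schedule of Events says: "Subjects who discontinue therapy will attend their regularly scheduled study visits to the end of the study". Protocol 10.3.1 collects adverse events to Visit 24, which is Month 37.

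**By-year displays.** The adverse event lists in SAP 6.12.1 include six displays by year of onset, starting with "TEAE by System Organ Class and Preferred Term by Year of Onset". SAP 6.11.2.3 adds flare frequencies and percentages by year. Neither states a denominator for each year. The default in SAP 6.3 is: "Percentages will be based on the number of non-missing observations out of the subject population unless otherwise specified".

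**The concern.** A rate is interpretable only when its events arise in the person-time below the line. Here the numerator is all events from two studies, and the only matching exposure definition stops at the last dose. A subject who stops drug soon after entering AURORA 2 at Month 12 can contribute about two years of further events and no further time. Stopping may well differ by arm, because protocol 5.6.1 links permanent discontinuation to rescue treatment as well as to toxicity. The rate would then be raised more in the arm that stops more, and if that were placebo, a true excess on voclosporin would be partly hidden.

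The by-year tables have the mirror problem. Protocol 5.2 requires 52 completed weeks of AURORA 1 treatment, so Year 1 is complete for everyone who entered AURORA 2. Years 2 and 3 lose subjects. With a fixed N, later percentages can fall although the risk has not, in a study whose primary objective is long-term safety.

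**Working it through.** **Inputs from the documents.** Planned treatment ends at Month 36 and adverse event collection at Month 37. AURORA 2 starts at Month 12. The AURORA 2 ITT and safety populations are each 216 (SAP 6.1). The documents give no stopping, loss or event rates by arm, so those below are assumptions.

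**1. The plan's own exposure example (SAP 6.9).** 364 + 136 + 100 + 150 + 345 = 1095 days, which reproduces. It includes 100 zero-dose days, so dosed days are 1095 − 100 = 995. The SAP's exposure is therefore time from first to last dose, including interruptions, and excludes only the time after the last dose. (Separately, the mean dose in that example does not reproduce: (1092 + 408 + 0 + 300 + 1035)/1095 = 2835/1095 = 2.59 capsules BID, or 40.9 mg per day, against the stated 2.34 and 37.03 mg. Those figures need reconciling but do not affect this point.)

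**2. All events over first-to-last-dose time.** Let a share s of an arm stop drug uniformly over Months 12 to 36, with everyone followed to Month 37 at an unchanged event rate. Mean exposure is 36(1 − s) + 24s = 36 − 12s months, so inflation = 37/(36 − 12s).

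| s | Exposure (months) | Inflation |
|---|---|---|
| 0% | 36.0 | 1.03 |
| 10% | 34.8 | 1.06 |
| 20% | 33.6 | 1.10 |
| 30% | 32.4 | 1.14 |
| 40% | 31.2 | 1.19 |

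**3. Effect on the arm ratio when the true ratio is 1.** Apparent ratio = (36 − 12s for placebo)/(36 − 12s for voclosporin).

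| Voclosporin stops | Placebo stops | Ratio |
|---|---|---|
| 30% | 30% | 1.00 |
| 20% | 30% | 32.4/33.6 = 0.96 |
| 30% | 20% | 33.6/32.4 = 1.04 |
| 10% | 40% | 31.2/34.8 = 0.90 |
| 40% | 10% | 34.8/31.2 = 1.12 |

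**4. Subject-based rate, if one is produced.** Over T = 3 years with first-event rate λ, subjects with an event per year of total exposure is [1 − exp(−3λ)]/3, which is below λ. At λ = 0.10 it is 8.6 per 100 years instead of 10. With a true rate ratio of 1.5, the ratio becomes [1 − exp(−4.5λ)]/[1 − exp(−3λ)] = 1.48, 1.40, 1.25 and 1.04 for placebo rates of 2, 10, 30 and 100 per 100 years. Ending each subject's time at the first event returns 1.50 throughout.

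**5. By-year percentages on a fixed N.** Assume a constant hazard of 0.3 per year and 15% of those remaining leaving uniformly during each of Years 2 and 3.

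- Year 1: 1 − exp(−0.3) = 25.9%.
- A subject who leaves during a year has an onset in it with probability 1 − 0.2592/0.3 = 13.6%.
- Year 2: 0.85 × 25.9% + 0.15 × 13.6% = 24.1%.
- Year 3: 0.85 × 24.1% = 20.5%.

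With N taken at the start of each year, Year 3 becomes 20.5/0.85 = 24.1%, so the series is 25.9%, 24.1%, 24.1%. The remaining small step comes from part-years, which a rate per 100 person-years removes.

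**The case against.** **The link to SAP 6.9 is inferred.** SAP 6.12.1.1 does not cite it. This stands, but no other definition covers both studies, and a programmer following the text would have to use it.

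**A window may exist.** The opening of SAP 6.12.1, where a treatment-emergent definition would normally sit, is not in the available text. The SAP also lists post-treatment deaths apart from treatment-emergent ones, and the sentence on all events may mean only that the studies are pooled. This stands, and the point is conditional on it. Against it, 6.12.1.1 speaks of all events where the neighbouring lists specify treatment-emergent ones, and protocol 13.9 gives the treatment-emergent rule a start but no end.

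**The calculation favours the concern.** It assumes full follow-up of stoppers and an unchanged rate off drug, whereas consent may be withdrawn. If the drug effect ends with the drug, with an on-drug ratio of 1.5, stopping of 20% voclosporin and 30% placebo, and follow-up of 37/12 = 3.083 years, the mismatched ratio is [(1.5 × 2.8 + 0.283)/2.8]/(3.083/2.7) = 1.40. All events over total follow-up give (1.5 × 2.8 + 0.283)/3.083 = 1.45. Also, step 2 needs stoppers to remain observed and step 5 needs subjects to leave, so the two sizes describe different subjects and do not add.

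**Two stronger readings are not supported.** A reader might infer that subject counts will be divided by total exposure. The sentence can equally mean a plain subject count beside an event rate, for which total time is the right denominator. A reader might also infer that arm ratios are already distorted. No ratio of exposure-adjusted rates is planned; the stated relative risk belongs to the AURORA 2 treatment-emergent summary.

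**The 6.3 default does not strictly fix the yearly N.** It refers to non-missing observations. Since an adverse event that did not occur is not a missing value, a fixed 216 is still the most natural result.

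**Conclusion.** The point holds as a mismatch in the plan as written, conditional on the unseen opening of SAP 6.12.1. If SAP 6.9 exposure is the denominator and no window applies, event rates are inflated by about 3 to 19% for assumed stopping of 0 to 40%. The 3% for completers is common to both arms and cancels in a ratio. A comparison of arms shifts only with differential stopping: by about 4% for a 10-point difference and by 10 to 12% for 30 points. Attenuation of a subject-based ratio is a risk only if such a rate is produced, and matters mainly for common events with a real difference. The by-year percentages can show an artificial decline; its size depends on the assumed hazard and loss.

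The consequence is bounded. SAP 3.1 makes the primary adverse event estimand a proportion of subjects, so these are supporting displays without a planned test. They are nevertheless where a reader will look for harm over time. The change should be made before the tables are programmed.

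**What to change.** In SAP 6.12.1.1, name the population and pair numerator and person-time explicitly: either events within a stated window after the last dose over that same window of time, or all events over total follow-up. If a subject-based rate is reported, end each subject's time at the first event of that term.

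For the year-of-onset adverse event tables and the by-year flare percentages in SAP 6.11.2.3, use the subjects under observation at the start of that year as N, and add the rate per 100 person-years within the year.

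The cost is SAP wording and programming. No new data are needed, since dose dates, visit dates and event onset dates are already collected.
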